## LIST OF ABBREVIATIONS

ACRONYM	DESCRIPTION
11-OH-THC	11-Hydroxy- $\Delta^9$ -tetrahydrocannabinol
AUDIT	Alcohol Use Disorder Identification Test
BAI	Beck Anxiety Inventory
CAT	Computerized Adaptive Test
CBC	Cannabichromene
CBD	Cannabidiol
CBD-A	Cannabidiolic Acid
CBG	Cannabigerol
CBG-V	Cannabigevarin
CBN-COOH	Carboxy- cannabinol
CI	Confidence Interval
Co-I	Co-Investigator
EMR	Electronic Medical Record
FACT-Cog	Functional Assessment of Cancer Therapy - Cognitive
FACT-G	Functional Assessment of Cancer Therapy - General
FDA	Food and Drug Administration
IIT	Investigator-Initiated Trial
HPLC-MS	Multianalyte high-performance liquid chromatography + tandem mass spectrometry
M	mean
MCQ	Marijuana Craving Questionnaire
Mg	milligram
N	Number of participants
NIDA	National Institute on Drug Abuse
NIH	National Institutes of Health
OCRST	Oncology Clinical Research Support Team
OR	Odds Ratio
PI	Principle Investigator
PSQI	Pittsburgh Sleep Quality Index
REDCap	Research Electronic Data Capture
STAI	State-Trait Anxiety Inventory
THC	$\Delta^9$ -tetrahydrocannabinol
THC-COOH	Carboxy- $\Delta^9$ -tetrahydrocannabinol
THC-V-COOH	Carboxy- $\Delta^9$ -tetrahydrocannabivarin
TLFB	Timeline Followback Substance Use Assessment
UCH	University of Colorado Hospital
VA	Veterans Affairs Medical Center

## PROTOCOL SUMMARY / SYNOPSIS

**Protocol Title:** *Effects of Cannabis Use in Cancer Patients: A Feasibility Study*

**Objectives:**

- ***Primary Objective:***  
The goal of this study is to determine the feasibility of a human observational study of orally administered *Cannabis* use among cancer patients, towards developing feasibility/pilot data in support of an R01 grant application to the National Cancer Institute. The primary objective will be to enroll 30 patients and demonstrate reasonable compliance with study procedures within fifty-four months of active recruiting.

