**Endpoint:**

  - ***Recruitment Outcomes:***  
Number of interested patients who contact the research team  
Number of eligible potential participants  
Number of enrolled eligible participants  
Number of study assessments completed by enrolled participants  
Number of participants who complete the study

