**Population:**

    - ***Sample size***
      - Maximum number of participants that can be enrolled is 150 (allow for screen failures)
      - Minimum number of participants to be enrolled: **30** (number of participants needed to answer scientific question/aims)
    - ***Gender***
      - Male and Female
    - ***Age Range***
      - 21-100
    - ***Demographic group***
      - Have a diagnosis of any solid tumor type who has or is undergoing either curative or palliative treatment
    - ***General health status***
      - Oncology Patients
    - ***Geographic location***
      - Denver/Boulder Area

**Phase:** Pilot

**Number of Participating Sites enrolling participants:** UC Central; UC Boulder

[figure not shown]

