## 2.2 RATIONALE

**2.2.1. Overview.** We submitted a grant to NIH/NCI using an observational design that is well established by the CUChange Lab to do a fully powered trial with cancer patients. While the reviewers noted that “the proposed research will provide much needed scientific data to the public, physicians, patients, and to the larger research community on the varying effects of different forms of *Cannabis* on cancer treatment-related symptoms and patient quality of life” they were concerned that “while the group is experienced with the methodology proposed, the lung cancer population is a new endeavor. The team is bolstered by inclusion of coinvestigator effort with experience in this population, but there are no pilot data to indicate proof-of-concept and feasibility of yielding a sufficient sample with reasonable compliance with procedures.” Thus, we seek to demonstrate proof-of-concept and feasibility.

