## 2.3 POTENTIAL RISKS AND BENEFITS

### 2.3.1 KNOWN POTENTIAL RISKS

- Human Subjects Involvement and Characteristics: Participants for the proposed research will be individuals who have been diagnosed with cancer of any solid tumor type and are interested in using *Cannabis* in the context of their cancer care. Participants' medical charts will be reviewed by our study physician, with the documented consent of the patient participant, to ensure their safety to engage in study participation. To account for expected attrition (20-25% based on our similar *Cannabis* studies) 150 participants will be recruited in total, though we anticipate that only 30 of these will complete the study.
- Sources of Materials: The source of the majority of research data will be the participants' responses to questionnaires or questions on interviews. Other research data will involve cognitive tests. Finally, we will obtain information on health status and current medications from HIPAA compliant review of electronic medical records accessed by the study team and our oncology co-investigators.
- Potential Risks: Potential risks are minimal. They include: **a)** Breach of confidentiality; **b)** Adverse effects of *Cannabis* such as intoxication, acute mood shifts, odd perceptual experiences, etc.; and **c)** The need for medical oversight in a cancer patient population.

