### 3 OBJECTIVES AND PURPOSE

The goal of this study is to determine the feasibility of a human observational study of orally administered *Cannabis* use among cancer patients with any solid tumor type, towards developing feasibility/pilot data in support of an R01 grant application to the National Cancer Institute. The primary objective will be to demonstrate the number of contacts necessary to enroll 30 eligible patients and demonstrate reasonable compliance with study procedures (see section 10.5.4) within fifty-four months of active recruiting.

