### 4.2 STUDY ENDPOINTS

#### 4.2.1 PRIMARY ENDPOINT

Our study endpoints are recruitment based. Please refer to the figure below.

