### 7.2.1 CLINICAL LABORATORY EVALUATIONS (RESEARCH PROCEDURES)

Pregnancy screening. A urine pregnancy screening test will be administered to all female potential study participants of child-bearing age after informed consent has been obtained at the Baseline visit to verify eligibility for the study. For the pregnancy screening, a trained research assistant will deliver a urine receptacle to the participant's home. The participant will then use the restroom in their home and return the receptacle to the research assistant to complete the urine test in the mobile laboratory.

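### The sample-size figures conflict: 20-25% attrition cannot take 150 recruited to 30 completing, and it is unclear whether 30 counts people enrolled or people completing

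*Combined protocol and SAP*

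**What the plan says.** The plan gives its numbers in five places.

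- **Synopsis, Objectives:** "The primary objective will be to enroll 30 patients and demonstrate reasonable compliance with study procedures within fifty-four months of active recruiting".
- **Section 3:** "The primary objective will be to demonstrate the number of contacts necessary to enroll 30 eligible patients", together with reasonable compliance, in the same 54 months.
- **Synopsis, Population:** "Maximum number of participants that can be enrolled is 150 (allow for screen failures", beside a minimum of 30 enrolled, described as the number needed to answer the aims.
- **Section 2.3.1:** after citing expected attrition of 20-25% from the group's similar studies, "150 participants will be recruited in total, though we anticipate that only 30 of these will complete the study".
- **Section 10.4:** 30 participants are to be recruited.

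Section 10.3.1 sets an 80% retention goal among enrolled participants and defines reasonable compliance as completing 75% of assessments.

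On who counts as enrolled, the synopsis endpoint list starts with "Number of interested patients who contact the research team". It then counts people eligible, people both enrolled and eligible, assessments completed, and completers. Section 7.2.1 places the pregnancy test for women of child-bearing age "after informed consent has been obtained at the Baseline visit to verify eligibility for the study".

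**The concern.** Section 2.3.1 is the only place that tries to derive a recruitment number from an attrition rate, and the derivation does not work. It also gives 150 a different reason from the synopsis, which cites screen failures. And it makes 30 the number completing, where the synopsis, Section 3 and Section 10.4 make it the number enrolled or recruited. Sections 2.3.1 and 10.4 use the same verb, to recruit, for 150 and for 30.

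Section 10.1 describes the endpoints as strictly recruitment based, so these counts are the study's main result. Two things depend on them: when recruitment is complete, and the denominator of the 80% retention goal. Someone can consent and then prove ineligible. If such a person counts as enrolled, the target of 30 is reached sooner and the retention percentage is lower.

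**Working it through.** **Inputs.** Attrition 20-25%, 150 recruited and 30 completing (Section 2.3.1); 150 maximum and 30 minimum enrolled (synopsis, Population); 30 enrolled or recruited within 54 months (synopsis Objectives, Section 3; Section 10.4 gives the 30); 80% retention goal (Section 10.3.1).

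**Step 1. Can 150 be reproduced from 30 completers and 20-25% attrition?** Number to enrol = completers / (1 - attrition).

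- 30 / 0.80 = 37.5, rounded up to 38
- 30 / 0.75 = 40

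The cruder inflation, completers x (1 + attrition), gives 36 and 38. Neither formula comes near 150.

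**Step 2. How many of 150 would complete?**

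- 150 x 0.80 = 120
- 150 x 0.75 = 112.5, about 113

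Thirty completing of 150 is 30/150 = 20%, a loss of 80%. That is not 20-25%.

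**Step 3. Can screen failures bridge the gap?** If 150 counts everyone consented or screened and 30 complete, then 38-40 must be enrolled. Screen failures would be 150 - 40 = 110 to 150 - 38 = 112, or 73-75% of 150. If 30 are enrolled, screen failures would be 120 of 150, or 80%. The documents give no screen-failure rate. Screen failures can therefore account for 150 as a ceiling, which is how the synopsis uses it. They are not the reason Section 2.3.1 gives.

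**Step 4. What follows if 30 is the number enrolled?**

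- At 20% attrition: 30 x 0.80 = 24 completing
- At 25% attrition: 30 x 0.75 = 22.5 completing
- Retention goal: 0.80 x 30 = 24

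The expected 22-24 is in line with the retention goal, which sits at its upper end. It is not 30.

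**Step 5. What depends on the choice?**

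| Meaning of 30 | To enrol | Expected to complete | Enrolments per month over 54 months |
|---|---|---|---|
| 30 enrolled | 30 | 22-24 | 30/54 = 0.56 |
| 30 completing | 38-40 | 30 | 38/54 = 0.70 to 40/54 = 0.74 |

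The second reading needs 8-10 more people, or 27-33% more (8/30 to 10/30).

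**Step 6. Does the definition of enrolled matter?** If 24 of 30 eligible participants are retained, the goal is exactly met at 80%. Count one post-consent screen failure as enrolled and it becomes 24/31 = 77%, which misses.

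**The case against.** The strongest reply is that the plan is clearer than this suggests. The synopsis endpoint list and Section 3 both attach eligibility to enrolment. Section 7.3.2 is headed as the enrolment and baseline session and places consent there. Most criteria are screened beforehand by telephone. The post-consent test in Section 7.2.1 applies only to women of child-bearing age, so few people may be affected. Most of this stands, and it is why the definition in the fix makes explicit what the plan implies. It does not settle the matter. No section says which event makes a person enrolled, the synopsis ceiling on those enrolled makes room for screen failures, and Section 13.3 makes acceptance depend on a physician review whose timing it does not state. Nor does the reply touch the arithmetic in Section 2.3.1.

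Two stronger readings are tempting, and the documents do not support them.

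- **A reader might infer that 30 in 54 months is too slow, or that omitting a benchmark rate for the larger study is a defect.** Section 2.2.1 gives the purpose, "feasibility of yielding a sufficient sample with reasonable compliance with procedures", but the documents state neither the size nor the duration of that study. The contact and enrolment counts are already planned. Section 4.2.1 says "Our study endpoints are recruitment based. Please refer to the figure below", and that figure is not available here, so a criterion in it cannot be excluded. The comparison could also be made in the grant application.
- **A reader might infer that the investigators expect to lose 80% of enrolled patients, contradicting their own 80% retention goal.** That compares completers among those recruited with a goal set for those enrolled. If 150 includes screen failures, the two percentages have different denominators.

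**Conclusion.** The inconsistency is real and can be shown from the plan's own figures. Attrition of 20-25% leaves about 113-120 of 150, and 30 completers require 38-40 enrolled. Thirty enrolled gives about 22-24 completers, consistent with the retention goal of 24 but not with 30 completing. The target therefore differs by 8-10 people according to which meaning is intended, and the retention percentage depends on whether screen failures are counted as enrolled.

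This takes the stated attrition to apply to everyone enrolled. It needs no assumption about the larger study. Thirty is not shown to be a poor size for a feasibility study. The matter is one of low severity: a correction of wording that the study could usefully make.

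**What to change.** 1. **Section 2.3.1:** make 150 the ceiling on people consented or screened, including screen failures, and remove its link to 20-25% attrition. Align the synopsis Population entry, which at present calls 150 a maximum enrolled.
2. **One target:** choose either 30 enrolled, with about 22-24 expected to complete, or 30 completing, with 38-40 enrolled. Use it in the synopsis (Objectives and Population) and in Sections 2.3.1, 3 and 10.4. The first choice needs fewer edits, because most of these places already treat 30 as the number enrolled or recruited.
3. **Definition:** state that enrolled means consented and confirmed eligible, and make that count the denominator of the 80% goal in Section 10.3.1. Report the number consented separately.
4. **Primary objective:** use the same wording in the synopsis and Section 3. Section 3 also refers to Section 10.5.4 for compliance, while the definition stands in Section 10.3.1 and the available text of Section 10 ends at 10.5.3. Correct that reference at the same time.

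Optionally, report enrolments per month with a 95% interval. Exactly 30 in 54 months would give 0.56, with exact Poisson limits 20.24/54 = 0.37 and 42.83/54 = 0.79. A benchmark against the larger study is not required.

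**Cost.** This is a wording amendment, which Section 13.2 sends to the ethics board for approval. It asks nothing more of patients. It adds a consented count to those already listed, and the expected number of completers may have to be stated as fewer than 30.

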**Endpoint:**

  - ***Recruitment Outcomes:***  
Number of interested patients who contact the research team  
Number of eligible potential participants  
Number of enrolled eligible participants  
Number of study assessments completed by enrolled participants  
Number of participants who complete the study

**Population:**

    - ***Sample size***
      - Maximum number of participants that can be enrolled is 150 (allow for screen failures)
      - Minimum number of participants to be enrolled: **30** (number of participants needed to answer scientific question/aims)
    - ***Gender***
      - Male and Female
    - ***Age Range***
      - 21-100
    - ***Demographic group***
      - Have a diagnosis of any solid tumor type who has or is undergoing either curative or palliative treatment
    - ***General health status***
      - Oncology Patients
    - ***Geographic location***
      - Denver/Boulder Area

**Phase:** Pilot

**Number of Participating Sites enrolling participants:** UC Central; UC Boulder

[figure not shown]
**PI: [name]**  
**Protocol #: 18-0836**  
**Version Date: May 31st, 2022**

**Description of Study**

**Agent:** Self-Administered *Cannabis*

**Study Duration:** Fifty-Four Months

## SCHEMATIC OF STUDY DESIGN

## 1 PARTICIPATING SITES

A complete and current listing of investigators, research personnel, research facilities and other study centers (if applicable) participating in this study will be maintained throughout the duration of this study on a **Protocol Contact List** form, incorporated herein by reference.

## 2 INTRODUCTION: BACKGROUND INFORMATION AND SCIENTIFIC RATIONALE

### 2.1 BACKGROUND INFORMATION

**2.1.1. Cannabis Use and Cancer.** The American Cancer Society ([www.cancer.org](http://www.cancer.org)) quotes a lifetime risk of invasive cancer of 42% in men and 38% in women in the USA. Consequently, with the emergence of medical *Cannabis* as a therapeutic option in many states, particularly for cancer treatment-related symptomatology, this population represents one of the largest opportunities for real world medical *Cannabis* use research. As of early 2017, twenty-nine states

and the District of Columbia have legalized medical *Cannabis* programs. Importantly, recreational use is now legal in several states, making *Cannabis* even more accessible to potential medical users *even without a doctor's explicit recommendation or prescription*. Recent polls indicate that 77% of Americans believe that *Cannabis* has legitimate medical purposes. Likewise, a recent poll of physicians in North America found that 76% would recommend the use of *Cannabis* to alleviate symptoms, specifically in the case of a patient suffering from advanced cancer and severe cancer treatment-related side effects. In addition, because of its potential to target multiple symptoms, it has been suggested that *Cannabis* might reduce polypharmacy among cancer patients. While there is a great deal of cultural support for medical *Cannabis* programs, cancer patients and doctors alike have very little scientific information on which to base decisions regarding whether or not to use *Cannabis* or which product, cannabinoid composition, or route of administration to use. This information is critical as some products may be more or less beneficial, or more or less harmful in this population. **Given the fact that acceptance of and access to *Cannabis* is rapidly increasing across the nation, research on the risks and benefits of legal market cannabis use in this vulnerable population should clearly be a high priority.** The bulk of research on the use of medical *Cannabis* in cancer focuses on physical symptom reduction, while in contrast almost no studies have examined the *psychological and cognitive* impacts of medical *Cannabis* on cancer patients. This lack of research is surprising, given that the importance of examining new strategies with the potential to improve quality of life in cancer care is well-recognized among clinicians.

As noted, research examining medical *Cannabis* use in cancer patients has focused primarily on the effects of *Cannabis* on the reduction of physical symptoms related to cancer and anti-cancer treatment (e.g., chemotherapy). Recent reviews of this literature suggest that there is some evidence that medical *Cannabis* and/or synthetic cannabinoids can alleviate nausea and vomiting, stimulate appetite, reduce pain, alleviate anxiety, and mitigate neuropathy in this population. Importantly, some studies have illustrated that *Cannabis* may be more effective and/or desirable than standard treatments for these symptoms. For example, a review of 30 randomized studies investigating antiemetic properties of *Cannabis* compared to either placebo or standard antiemetics found that oral cannabinoids were more effective at reducing nausea and vomiting, and in these studies, between 38 and 90% of patients reported that they preferred the cannabinoids. While its antiemetic properties are clear, much less is known about other potential beneficial effects.

The current state of the research on *Cannabis* is fraught with important limitations. Most relevant to the current proposal is the fact that much of the research on cannabinoids in cancer treatment examines the effects of synthetic cannabinoids administered in capsule form (e.g., nabilone, dronabinol). However, given the changing legal status and availability of *Cannabis* both recreationally and medicinally, it is increasingly the case that cancer patients who use *Cannabis* are using it in plant derived form. While there are a vast number of products available in state-regulated medical and recreational markets, there is very limited research on how these new products might influence the consumer. *Cannabis* in its plant form contains more than 60 different cannabinoids, and the potencies of each vary significantly across strains. One of these cannabinoids, cannabidiol (CBD) may actually mitigate detrimental psychological effects of the more well-known and psychoactive cannabinoid, Δ9-tetrahydrocannabinol (THC). Yet most published research on *Cannabis* in cancer care equates effects of isolated synthetic THC to the far more complex plant form. The current proposal seeks to assess the feasibility of conducting a fully-powered study of the effects of plant-derived legal market *Cannabis* as used

by current cancer patients. Specifically, we wish to determine whether it is feasible to appraise the effects of orally administered *Cannabis* products among a cancer patient group by determining whether this group is willing to participate in all necessary components of a study examining how differing ratios of cannabinoids in cannabis products (based on type of product strain used) relate to symptom relief, quality of life, and cognitive measures.

**2.1.2. Psychological effects of *Cannabis* use in cancer patients.** There is some research that suggests the potential for positive psychological effects of *Cannabis* use that may improve quality of life. For example, some of the effects that are commonly described as adverse or harmful (e.g., feeling “high”, euphoria, sleepiness), may be reframed as positive effects for those suffering from cancer and the side effects of treatment (i.e., mood elevation, reduced anxiety, improved sleep quality). One study examined the effects of medical *Cannabis* on psychological symptom management by interviewing Israeli cancer patients before and 6-8 weeks after they received a medical *Cannabis* license, and found reductions in self-reported mood disorders, sleep disorders, and pain, as well as reduced use of pain medication and depression/anxiety medication after initiation of medical *Cannabis* use. Given these findings, the study authors concluded that medical *Cannabis* may be an important contribution to palliative cancer care.

At the same time, it is important to acknowledge the potential negative effects. Specifically, the literature is fairly clear that acute use of *Cannabis* temporarily compromises cognitive function. For example, one study observed impaired performance on an executive function task and two motor control tasks after a 13% THC dose of *Cannabis*. On the other hand, the evidence is mixed regarding the long-term effects. Notably, this evidence base is somewhat limited in that relatively few researchers have examined these effects, and results of such studies have in some cases been inconclusive or have important limitations (including studying only the effects of very low doses of THC that are rarely used in the real world). Regardless, it is nearly inevitable that cancer patients are faced with both self-regulatory challenges (i.e., adhering to complicated drug regimens, healthy eating, exercising to reduce fatigue) as well as cognitively taxing decisions (e.g., weighing pros and cons of treatment options) that rely on high-level working memory and executive function processes that may be influenced acutely by *Cannabis* use. Further, one of the greatest concerns of cancer patients and survivors are changes to their cognitive abilities. Research using traditional neuropsychological assessment has documented deficits in processing speed, attention/working memory and episodic memory. Moreover, cancer patients’ subjective reports of cognitive difficulties are often greater than the deficits when compared to performance on objective tests. Finally, there is a large body of research demonstrating that cancer patients may experience reduced cognitive functioning due to the effects of chemotherapy. Thus, it is essential to examine the impact of *Cannabis* use on both objective and subjective cognitive function in this already-vulnerable population.

**2.1.3. Synergistic effects of multiple cannabinoids on pain, anxiety, and insomnia.** It is worth noting that pain, anxiety, and insomnia are three of the most common complaints among cancer patients and are also the three most common conditions cited for use of medical *Cannabis*. Importantly, an expert panel convened by the National Academies of Sciences, Engineering, and Medicine concluded in their 2017 report that there was conclusive evidence that *Cannabis* is effective for treatment of chronic pain, moderate evidence for its effect on sleep outcomes, and limited evidence for effects on anxiety. They also concluded that there is conclusive evidence for *Cannabis* effectiveness at treating chemotherapy-induced nausea and vomiting, however this was the only symptom domain where research has been conducted primarily or exclusively with

cancer patients. Further, much of the existing research has been conducted with synthetic individual cannabinoids. Thus, research on pain, insomnia, and anxiety among cancer patients and using products widely available in the legal market is critically needed. Currently, relief from chronic pain is by far the most common condition cited by patients for use of medical *Cannabis* in U.S. states with legal markets; 87%-94% of self-reported medical *Cannabis* users report using *Cannabis* for relief of a pain condition. Treatment of anxiety and insomnia are the next most common medical uses. In addition, there is some evidence that individuals are replacing the use of traditional pain, mood, and sleep medications with *Cannabis*. For example, one recent study reported survey data suggesting that medical *Cannabis* use in pain patients was associated with a 64% decrease in opiate use. A second study recently observed significantly lower opiate overdose deaths in states with medical access to *Cannabis*. Similarly, recent analyses of prescription data in states with medical access to *Cannabis* suggest a significant reduction in the prescription of medications for pain, anxiety, and sleep dysfunction.

Pain. Across five high quality reviews conducted in the past four years, results were consistent in suggesting that cannabinoids demonstrate an effect on pain. For example a rigorous, systematic review by Whiting et al covered 28 chronic pain studies (2454 participants) primarily conducted in Canada or Europe. Twenty-two of these studies evaluated plant-derived cannabinoids (cannabis extract mouth spray or nabiximols n=13, plant flower that was smoked or vaporized n=5, oramucosal spray n=3, oral THC n=1) while 5 studies evaluated synthetic THC (i.e., nabilone). All of the selected studies included either an active comparator or placebo control. Analyses across studies that evaluated the effects of inhaled plant-derived *Cannabis* suggested a statistically significant effect on the odds of a 30% or greater improvement in pain (OR = 1.41). The largest single effect size presented across the reviews was observed with inhaled *Cannabis* on pain [e.g. OR, 3.43; 38]. Consistent with this, an average OR of 3.22 (CI: 1.59 to 7.24) was found across 9 doses of inhaled THC tested across five studies. While the analgesic properties of THC are the most widely studied, pharmacological and clinical data suggest that cannabidiol (CBD) is another primary cannabinoid that may work synergistically with THC in a multi-target analgesic approach to pain relief. For example, nabiximols which are an administration of a plant-based mixture of THC and cannabidiol (CBD) via mouth or nasal spray were associated with significant reductions in numerical pain ratings across the available studies.

Anxiety/affect. There is evidence demonstrating that *Cannabis* use is associated with increased anxiety and anxiety disorders. However, other data, including our own prospective work, suggests that *Cannabis* use may be protective for anxiety and may decrease the chances of developing an anxiety disorder. A number of studies have found that *Cannabis* acutely increases positive mood and measures of reward even when using a “balanced placebo” design to control for expectancy effects. This finding is consistent with a growing body of evidence from animal models suggesting that *Cannabis* has anxiolytic effects. Overall, however, research studies have largely ignored the fact that *Cannabis* exists in different forms with differing ratios of THC to CBD and have not characterized the effects of *Cannabis* as the compound action of different cannabinoids that vary in terms of their pharmacological effects. Two primary cannabinoids, THC and CBD, may have opposing effects with regard to anxiety. Importantly, THC is thought to be acutely anxiogenic, while treatment with CBD has anxiolytic effects without the experience of a “high”. Clarifying the anxiolytic effects of specific strains that differ in their cannabinoid composition may explain these discrepant findings.

Sleep. THC has been shown to dose dependently reduce wake time and increase Stage 4 sleep across human and animal studies. Whereas it has been well established that THC promotes sleep, contradictory results on the effect of CBD on sleep have been reported. For instance, an early study found a diminution in sleep after systemic administration of CBD, whereas other work showed an improvement in sleep in insomniacs after using CBD. Much of this work has been done, again, with synthetic oral forms of THC and CBD in isolation, leaving a limited knowledge base on the effects of the synergistic effects of plant-derived cannabinoids in common forms of administration.

A 2017 survey study of cannabis use among cancer patients showed that pain, stress, and sleep were all identified as reasons for *Cannabis* use. Though the study did not ask specifically about quality of life, over half (51%) of patients felt that *Cannabis* was a “major benefit” while another 39% agreed it was a “moderate benefit.” It is logical to assume, therefore, that to the extent that *Cannabis* alleviates negative symptoms from cancer and cancer-treatment, it should also increase overall quality of life. Also, while there is evidence to suggest that *Cannabis* may be effective for pain, anxiety, and sleep—and consequently quality of life—it is not clear whether these effects are driven by one of the primary cannabinoids (THC or CBD) or the synergistic combination of the two. Overall, very little is known about the efficacy, dose, routes of administration, or side effects of commonly used *Cannabis* products in the U.S that come in a variety of potencies and cannabinoid contents, nor critically how these products may work differently in cancer patients.

**2.1.4. THC and cognitive impairment.** A number of studies indicate that *Cannabis* produces acute cognitive impairment, especially relating to memory and attention during intoxication and possibly for hours to days after use. For example, studies that were published as early as the 1970’s suggest that *Cannabis* disrupts immediate and delayed free recall of information e.g., 50,51. Recall of words from a list is one of the most common approaches to demonstrating the effect of THC on recall performance e.g., 52. Studies have also suggested working memory may be the most sensitive to the acute effects of *Cannabis* *see* . Among the studies that included two THC concentrations, higher doses mostly yielded greater cognitive impairment. In neuroimaging work, *Cannabis* users showed differential brain response to an associative memory task while under the influence of THC compared with a placebo. Specifically, THC attenuated brain activity in the insula, right inferior frontal gyrus (IFG) and left middle occipitals gyrus during encoding, and increased network-wide activity during recall. Taken together, these results suggest that THC has a negative effect on the neurocognitive processes involved with encoding, and neural activation changes during recall likely reflect a compensatory mechanism for the affected encoding. That is, the memory system as a whole must work harder in order to account for the cognitive deficits induced by THC. In sum, the literature suggests that acute administration of *Cannabis* impairs the encoding and retrieval of information, albeit to a modest degree, and these effects may be dose-dependent on THC level. Further, this *Cannabis*-induced cognitive impairment can last from hours to days after use and potentially longer in heavy chronic users. Thus, the potential cognitive side effects of regular use of current *Cannabis* products are highly relevant to cancer patients, who may use *Cannabis* on a regular basis to treat their symptoms but who also want to maintain as much cognitive function as possible.

**2.1.5. Does CBD mitigate the harmful cognitive effects of THC?** Clearly, the evidence suggests that acute *Cannabis* use is associated with at least modest cognitive impairment. However, almost all of this research was conducted with low potency cannabis provided by the

government and almost all of this research was focused on the effect of one particular cannabinoid, namely THC. The effects of other primary cannabinoids, such as CBD, are important to consider when interpreting the harmful effects of *Cannabis* use, especially given that *Cannabis* includes more than 80 additional phytocannabinoids. Products commonly available in states like Colorado differ dramatically on the potency of these cannabinoids. As noted previously, studies suggest that THC is associated with memory and other cognitive impairment. Conversely, analyses suggest that CBD may attenuate the negative effects of THC on cognition and other measures. Most of the work on CBD has involved the administration of THC and CBD in synthetic pill form. Much less is known about the combined effects of THC and CBD when using cannabis in the forms commonly available in dispensaries across the U.S. This is a high priority area of research in terms of understanding how to reduce the potentially harmful effects of cannabis use in cancer patients.

[figure not shown]
**2.1.6. Limitations of existing literature.** Most of the *Cannabis* products that are sold in state regulated markets bear little resemblance to the products that are available for research from NIDA at the federal level in the U.S. For example, per Figure 1, the most recently available data in Colorado alone show that >600,000 edible units of *Cannabis* were sold across medical and recreational dispensaries each month of 2015, nearly a 50% increase from the monthly data reported for 2014, the first year of legal *Cannabis* sales in our state. Data also suggest that medical *Cannabis* patients

are more likely to use edible products than recreational users.

Importantly, using *Cannabis* in orally administered form represents a very different way to use cannabis, in part because in contrast to smoked forms of *Cannabis*

which produce acute effects that begin to diminish rapidly after consumption (blood levels dramatically decrease within 15 minutes of smoking), orally administered *Cannabis* produces prolonged effects that last at least 4 hours post-consumption. This in part explains their increased use in patients who seek sustained relief from symptoms. However, no data are available to understand the mechanisms or effects of orally administered *Cannabis* of various potencies and cannabinoid ratios. Thus, while the use of particular forms of *Cannabis* in cancer patients is supported by well-controlled clinical trials as reviewed above, very little is known about the efficacy, dose, routes of administration, or side effects of *commonly available and increasingly used orally administered Cannabis products*. In the case of cancer patients, our clinician co-investigators instruct their patients not to inhale *Cannabis*, but instead to use orally administered forms. More research is desperately needed given the increased availability of *Cannabis* across the nation and the lack of any research in the U.S. on the beneficial or harmful effects of orally administered *Cannabis* for cancer patients.

Figure 1. State of Colorado Official Reporting on Edible Cannabis Sales

